## 4.4 End of Study Definition

A participant is considered to have completed the study if he or she has completed the 90-day visit shown in the SoA, see Section 1.3.

# 5 STUDY POPULATION

## 5.1 Inclusion Criteria

1. Age 18 years and older
  2. Suspected anterior circulation acute ischemic stroke
  3. Presenting NIH Stroke Scale score  $\geq 6$
  4. Favorable baseline neuroimaging consisting of all of the following:
    - a. ASPECTS of 6 or more on CT (or ASPECTS of  $\geq 7$  on MRI)
    - b. Favorable perfusion imaging on CT perfusion (CTP)/MR-perfusion weighted imaging (PWI) consisting of all of the following:
      - i. Mismatch ratio of penumbra:core  $>1.2$
      - ii. Mismatch volume  $>10$  cc
      - iii. Core  $<70$  cc
-

5. Able to receive assigned study drug within 4.5 to 24 hours of stroke onset or last known well.
6. Able to receive assigned study drug within 90 minutes of qualifying perfusion imaging.\*
7. Informed consent for study participation obtained from participant or their legally authorized representative.

\*Study drug administration is encouraged within 60 minutes after qualifying perfusion image but is allowed up to 90 minutes. After 90 minutes, another perfusion image to ensure that inclusion criteria are met is required.

## **5.2 Exclusion Criteria**

1. Plan to receive endovascular treatment.
  2. Received or plan to receive IV thrombolysis.
  3. Pre-stroke modified Rankin score >2.
  4. Previous treatment with TS23 or known previous allergy to antibody therapy.
  5. Known pregnancy, women who are breastfeeding or plan to breastfeed within 3 months of receiving TS23 or have a positive urine or serum pregnancy test for women of childbearing potential.
  6. Known previous stroke in the past 90 days.
  7. Known previous intracranial hemorrhage, intracranial neoplasm, subarachnoid hemorrhage, or arterial venous malformation.
  8. Known active diagnosis of intracranial neoplasm.
  9. Clinical presentation suggestive of a subarachnoid hemorrhage, even if initial CT scan was normal.
  10. Surgery or biopsy of parenchymal organ in the past 30 days.
  11. Known trauma with internal injuries or persistent ulcerative wounds in the past 30 days.
  12. Severe head trauma in the past 90 days.
  13. Persistent systolic blood pressure >180mmHg or diastolic blood pressure >105mmHg despite best medical management.
  14. Serious systemic hemorrhage in the past 30 days.
  15. Known hereditary or acquired hemorrhagic diathesis, coagulation factor deficiency, or oral anticoagulant therapy with International Normalized Ratio (INR) >1.7.
-

16. Platelets <100,000/mm^3.
17. Hematocrit <25 %.
18. Elevated aPTT above laboratory upper limit of normal.
19. Creatinine > 4 mg/dl, or patients receiving renal dialysis, regardless of creatinine.
20. Received heparin or low molecular weight heparins (such as Dalteparin, Enoxaparin, Tinzaparin) in full therapeutic dose within the previous 24 hours.
21. Received Factor Xa inhibitors (such as Fondaparinaux, apixaban or rivaroxaban) within the past 48 hours.
22. Received direct thrombin inhibitors (e.g., argatroban, dabigatran, bivalirudin, desirudin, lepirudin) within 48 hours.
23. Received glycoprotein IIb/IIIa inhibitors within the past 14 days.
24. Known pre-existing neurological or psychiatric disease, which would confound the neurological/functional evaluations.
25. Current participation in another research drug treatment protocol (i.e., participants could not start another experimental agent until after 90 days).
26. Concurrent acute myocardial infarction, pulmonary embolism, deep venous thrombosis, or other thrombotic event that requires anticoagulation or anti-platelet treatment.

### **5.3 Screen Failures**

The population to be screened for the trial is defined as AIS patients presenting within 4-23 hours of last known well and who did not (or are not planned to) receive IV thrombolysis or endovascular treatment as standard clinical care. Among these, patients who are not consented are considered “screened, not consented.” Patients who are consented but are not randomized due to study imaging ineligibility or other reasons, are considered “consented, not randomized.” A participant, who is both randomized **and** received study drug initiation, is in the modified Intent-to-Treat (mITT) population. To ensure transparent reporting of screen failure participants, to meet the Consolidated Standards of Reporting Trials (CONSORT) publishing requirements, and to respond to queries from regulatory authorities, we will collect demography, screen failure details, and eligibility criteria.

### **5.4 Strategies for Recruitment and Retention**

The target sample size for SISTER trial is 300 participants in the mITT population enrolled over 36 months at 50 active sites at a given time (average accrual rate of 2.6 patient per site per year). All 50 active sites participating in the trial will screen and enroll consecutive patients who meet the trial criteria. The study personnel will not discriminate based on age, gender, race/ethnicity. Participants will be screened and enrolled in the emergency room of all participating comprehensive stroke centers.

---

The study personnel will work with local treatment teams to identify potential participants. The strategies of such identification will be outlined in the Manual of Procedures document as well as local site-level Standard Operating Procedures (SOPs) document.

By the nature of the condition, a considerable portion of patients with acute ischemic stroke may experience acute cognitive dysfunction. They are a vulnerable population. Inclusion of these patients is required to optimally inform safety and efficacy profile of the study drug for all acute stroke patients that meet the study criteria and to generate results that are generalizable. Exclusion of all patients with cognitive impairment at the time of enrollment will result in a study population that is not representative of AIS patients presenting within the 4.5-24-hour time window. Our team has extensive experience in undertaking investigations that involve vulnerable patients, and we will apply our expertise in minimizing risks for these study participants. Our study team has extensive experience with surrogate consent process as well. Because SISTER is a phase 2 trial testing safety of a novel drug, we will exclude pregnant women due to potentially unknown risks of the medication. Other special populations, such as fetuses, neonates, prisoners, and children, will not be eligible for inclusion.

## **6 STUDY INTERVENTION**

### **6.1 Study Intervention(s) Administration**

#### **6.1.1 Study Intervention Description**

TS23 is an IgG2 chimeric antibody that inactivates human a2AP. TS23 is expected to enhance the dissolution of thrombi by removing the inhibitory effects of a2AP on the fibrinolytic process.

Participants enrolled in SISTER should not receive antithrombotics for at least 24 hours after study drug administration.

The study order sets will specifically include an order not to administer antithrombotics within the first 24 hours after study drug administration. This will also be closely monitored as participants will be admitted to the intensive care unit setting for at least first 24 hours after drug admission.

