TS23 inhibited a2AP activity in all participants, in a dose-related fashion, with maximum effects in the initial blood samples after IV dosing (Figure 6A). The duration of inhibition of a2AP was also dose related. a2AP activity was  $\sim$ >50% inhibited for hours to 4 days at dose 2.5 to 7.5 mg/kg. TS23 immediately activated fibrinolysis after dosing and increased D-dimer levels relative to baseline levels; D-dimer levels were higher in cohorts receiving higher doses of TS23 (Figure 6B). (D-dimer is a specific biomarker that indicates endogenous thrombus dissolution, even in normal, asymptomatic individuals). In addition, clots formed *ex vivo* from subject plasma obtained 24h after TS23 administration rapidly dissolved in a dose-dependent fashion, while control clots from normal blood donors did not dissolve within 120 min, the maximum time of monitoring. Thus, TS23 safely engaged and inactivated a2AP, in a dose-related fashion, triggering endogenous fibrinolysis *in vivo* and clot dissolution *ex vivo*.

Figure 6. Dose-related Effects of TS23 on a2AP Activity and D-dimer Levels in Humans

A) a2AP inhibition was measured in a clinically validated plasma assay at baseline and at the indicated time points following a dose of TS23. B) D-dimer levels were measured in participants at baseline and at the indicated time points following a dose of TS23. Means  $\pm$  SE are shown for each dose cohort.

Please see the current version of the [Investigator's Brochure](#) for further information on the Phase 1 Clinical study results for TS23 (a2AP-I).

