### **2.5.3 Assessment of Potential Risks and Benefits**

The proposed strategy for SISTER has gone through stages of review, critique, and revision from experts in the fields of stroke neurology, cardiology, and biostatistics. The inclusion and exclusion criteria are specifically chosen to only exclude conditions that may require special safety considerations for thrombolytics. The imaging selection component adds another layer of protection by ensuring that patients will only be enrolled that have significant salvageable brain tissue, and minimal amount of irreversible injured tissue (which is most likely to cause intracranial bleeding). The Multiple Principal Investigators team (MPIs), Independent Medical Monitor, and DSMB will closely and comprehensively monitor pre-specified safety events, AEs, SAEs and unanticipated problems (UPs), according to plans outlined in the Data and Safety Monitoring Plan attachment. They will be reported to the IRB and the sponsor as outlined in the protocol, who may suggest study modifications as appropriate to protect human participants. After the study drug infusion, patients will be monitored for immediate infusion reactions in a high acuity hospital setting for prompt identification and treatment.

---

Further, the study drug will be shipped and maintained under strict conditions according to our FDA-approved IND. We will strictly adhere to the study protocol, collect high-quality data, and thoroughly train and, periodically retrain, all research and clinical personnel involved with the study regarding the details of study protocol and procedures. During the study period, all patients will receive care according to the local and most recent acute stroke guidelines. Study personnel will be readily available to answer questions at any time during the study course. The small risk for violation of confidentiality will be minimized by training all study personnel with the web-based Responsible Conduct of Research Training Program.

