## **Adverse Reactions or Undesirable Effects**

TS23 will augment fibrinolysis and, similar to other thrombolytic agents, bleeding will be the most commonly anticipated AE. The bleeding events observed in the phase 1 human volunteer study were minor in nature, were transient and clinically inconsequential, did not require medical intervention, and were categorized as grade 1 events. Currently, there are no data available in such patients with active

---

illnesses who also may receive concomitant antithrombotic therapy. In pre-clinical studies, a surrogate a2AP-I for TS23 did not increase surgical bleeding in mice when used in combination with rivaroxaban, low molecular weight heparin or aspirin, by comparison to these agents alone (see [Investigator's Brochure](#)). However, in patients receiving concomitant antithrombotic therapy, the risk of bleeding may be higher. In case of severe bleeding requiring therapy, appropriate medical and surgical treatment should be instituted and antifibrinolytic agents such as epsilon amino caproic acid (Amicar) or tranexamic acid (Lysteda) may be considered, if clinically indicated, and used according to the package inserts (see Overdose, below).

TS23 is a chimeric monoclonal antibody and consequently a rare possibility of immunogenic response or infusion reaction exists. No infusion reactions were observed in the phase 1 human volunteer study. Furthermore, such reactions usually are expected when a subject receives a second or repeat dose of such therapy.

Clinical data from the only study with TS23 to date has not indicated any significant safety concerns, with a low number of treatment emergent adverse events (TEAEs) and no trends in the nature and/or severity of TEAEs detected. No deaths or treatment-related SAE have occurred in the development program. Observed bleeding TEAEs have been associated with venipuncture and have been of mild severity.

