## 8.1 Baseline

Patients presenting with acute ischemic stroke will be evaluated by a stroke team physician, in accordance with institutional practice, to establish study eligibility. All consecutive patients meeting study entry criteria will be enrolled in the trial.

Participants enrolled in SISTER should not receive antithrombotics for at least 24 hours after study drug administration.

The study order sets will specifically include an order not to administer antithrombotics within the first 24 hours after study drug administration. This will also be closely monitored as participants will be admitted to the intensive care unit setting for at least first 24 hours after drug admission.

The following data will be documented at the baseline evaluation for randomized patients:

- Demographics: Age, sex, race/ethnicity
  - Medical history regarding presence of concomitant medical conditions (e.g. hypertension, diabetes, hyperlipidemia, atrial fibrillation, prior ischemic stroke, prior hemorrhagic stroke, current or past smoking)
  - Vital signs: Systolic and diastolic arterial blood pressure; heart rate, temperature
  - Concomitant medications at time of stroke onset (anticoagulation, antiplatelets, antihypertensives, statins, antidiabetics, cholesterol reducers)
  - Pre-stroke functional state: pre-stroke modified Rankin Scale, pre-stroke ambulatory status (independent, with assistance, unable)
  - Laboratory Evaluation
    - Measurement within 12 hours prior to study drug administration (if there are multiple measurements, then consider the latest measurement)
      - SOC: aPTT, PT with INR, CBC, platelet count.
    - First measurements upon presentation to study hospital, within 2-3 hours of study drug administration):
      - SOC: Glucose, creatinine
    - First value collected during hospitalization:
      - SOC: Hemoglobin A1C, Lipid Panel containing total cholesterol, HDL, LDL & triglyceride.
  - Neurologic Deficit: NIHSS upon arrival to the study hospital
-

- Brain and Vascular imaging at presentation:
    - CT or MRI
    - CTA or MR angiography (MRA)
    - CTP or MRI-PWI, if applicable per institutional practices
  - Initial Workflow Time Metrics: Date and time of:
    - Last known well (LKW)
    - Symptoms first observed (SFO)
    - Outside hospital (OSH) date/times (if patient first presented to an OSH):
      - Arrival at OSH (“Door-In”)
      - Departure from OSH (“Door-Out”)
    - Study Hospital date/times:
      - Arrival at Study Hospital

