## 8.4 30 ( $\pm 4$ ) Hours Post Study Drug Administration

- Research related labs:
    - Fibrinogen, PT/INR, aPTT to be processed and resulted at site
    - a2AP, and MMP-9 levels and PK studies to be processed and frozen. This will be shipped to the central laboratory
  - SOC Labs:
    - CBC
-

- NIHSS assessed by blinded, certified rater
  - Basic metabolic panel (glucose, calcium, sodium, potassium, carbon dioxide, and chloride, BUN creatinine) at 30 ( $\pm 4$ ) hours post study drug administration if done as standard of care
  - Vital Signs
  - Non contrast CT Brain (reading will be performed centrally) (**Please note that an MRI cannot substitute for the CT**)
    - ASPECTS score
    - Any radiologic hemorrhage (further classified as SAH, HI1, HI2, PH1, PH2, RIH, IVH, SDH, EDH) on CT
  - CTA or MRA head (required only if visible vessel occlusion present on the baseline CTA or MRA per site read).
    - Presence of a visible vessel occlusion
    - Location of vessel occlusion (per the central reader): ICA, M1 MCA, M2 MCA, M3/M4 MCA, A1 ACA, A2-5 ACA, VA, BA, P1 PCA, P2 PCA, P3/4 PCA, PICA, AICA, SCA, Other
  - CT/MR perfusion
    - Perfusion lesion volume (volumes of regions with  $T_{\max} > 6$  sec and  $> 10$  sec on CTP or PWI MR)
    - Ischemic core lesion volume (on CTP -volume of region with  $rCBF < 30\%$ ; on DWI-volume of region with  $ADC < 620 \times 10^{-3}$  mm/s)
    - If the participant underwent CT perfusion at baseline, then CT perfusion should be obtained at 30 ( $\pm 4$ ) hours.
    - If the participant underwent MR perfusion at baseline, then MR perfusion should be obtained at 30 ( $\pm 4$ ) hours.
  - Symptomatic intracranial hemorrhage [symptomatic ICH, as per SITS-MOST definition (a local or remote type II parenchymal hemorrhage within 30 ( $\pm 4$ ) h after treatment associated with a  $\geq 4$ -point deterioration on the NIHSS score from baseline or from the lowest score from baseline to 24 hours, or leading to death.)] ([Wahlgren, Ahmed et al. 2007](#))
  - Major non-ICH systemic hemorrhage
  - Clinically relevant systemic hemorrhage
-

- AE
- SAE
- UPs

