### **8.5 72 Hour Visit / Discharge (+/-12 hrs.) (whatever comes first)**

- NIHSS
- Standard of Care anti-thrombotics started by end of day 2

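### The antithrombotic hold may end at 24 h, 2 to 10 h before an on-time 30 (±4) h CT, and the protocol does not require that CT to be read at the site first

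*Protocol*

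**What the plan says.** The hold appears in Section 6.1.1 and again in Section 8.1 of the protocol: "Participants enrolled in SISTER should not receive antithrombotics for at least 24 hours after study drug administration". It is enforced through the order set: "The study order sets will specifically include an order not to administer antithrombotics within the first 24 hours after study drug administration". Both are stated purely in time since dosing.

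The follow-up CT that supplies the primary safety endpoint is scheduled at 30 (±4) h (Sections 1.1, 8.4 and 9.1). Section 8.4 lists it as "Non contrast CT Brain (reading will be performed centrally"), and Section 9.1 has a blinded neuroradiologist determine ICH on the uploaded scan.

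Two other statements bear on what happens after 24 h. Section 2.5.3 says that "all patients will receive care according to the local and most recent acute stroke guidelines". Section 8.5, the 72-hour visit, lists "Standard of Care anti-thrombotics started by end of day 2". Neither mentions the CT.

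On risk, Section 6.1.1 (Adverse Reactions or Undesirable Effects) says that "in patients receiving concomitant antithrombotic therapy, the risk of bleeding may be higher". Section 2.4 reports drug activity at and beyond 24 h: clots from "subject plasma obtained 24h after TS23 administration rapidly dissolved in a dose-dependent fashion", and a2AP activity was more than about half "inhibited for hours to 4 days at dose 2.5 to 7.5 mg/kg".

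**The concern.** The summary of changes gives lower bleeding risk as a reason for adding the hold. A hold defined only by the clock can lapse before anyone has looked for hemorrhage. A participant with a silent hemorrhage could then receive an antithrombotic within protocol, hours before the scan that would show it, while TS23 may still be active.

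The protocol itself does not treat silent hemorrhage as benign: Sections 2.1 and 3.3 link asymptomatic or any ICH to worse outcome. TS23 is also being given to stroke patients for the first time (Section 4.2), and Section 6.1.1 reports no human interaction data. What is at stake is participant safety in the hours between the end of the hold and the CT, rather than the validity of the comparison between arms.

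**Working it through.** The protocol gives no figure for this gap, so there is none to reproduce. The check is interval arithmetic on its stated times, followed by a search for any rule that closes the gap.

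**Inputs**
- Minimum hold: 24 h after study drug (Sections 6.1.1 and 8.1).
- CT window: 30 ± 4 h (Sections 1.1, 8.4 and 9.1). Section 3.2 prints ±44 for the same endpoint, which I take as a misprint.
- Infusion time: about 15 min, or 0.25 h (Section 6.1.2).

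**Step 1: CT window.** Earliest 30 − 4 = 26 h; latest 30 + 4 = 34 h.

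**Step 2: gap = CT time − 24 h.**

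| On-time CT | Gap after earliest end of hold |
|---|---|
| 26 h | 26 − 24 = 2 h |
| 30 h | 30 − 24 = 6 h |
| 34 h | 34 − 24 = 10 h |

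**Step 3: sensitivity to the time origin.** If the hold runs from the end of the infusion and the CT from its start, the gap is 2 − 0.25 = 1.75 h to 10 − 0.25 = 9.75 h. The conclusion is unchanged.

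**Step 4: does any other text make antithrombotics wait for the CT?**
- Section 1.3: the 30 h CT may be standard of care or research. No link to antithrombotics.
- Section 2.5.3: general guideline care. No CT condition.
- Section 5.2, exclusion 26: removes patients with a concurrent thrombotic event needing anticoagulant or antiplatelet treatment. This makes an early urgent start less likely but does not order the CT first.
- Section 6.5.1: antifibrinolytic rescue, triggered by symptomatic ICH or major systemic bleeding. A silent hemorrhage does not trigger it.
- Section 7.1: the investigator decides on management when a clinically significant finding is identified. It acts only once the finding is known.
- Section 8.4: central reading of the CT. No site read for hemorrhage is required, although the same section relies on a site read of the baseline angiogram to decide whether a follow-up angiogram is needed.
- Section 8.5: an antithrombotic line with no CT condition and no definition of day 2.

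None of these closes the 2 to 10 h gap.

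**Step 5: after the change.** With the start conditional on a locally read CT, the earliest routine start moves from 24 h to 26–34 h plus reading time, and the gap becomes zero apart from the stated exceptions.

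**The case against.** The strongest reply is that 24 h is a floor. The protocol does not tell sites to start antithrombotics at 24 h, and a site that waits for the CT complies fully. Care after 24 h follows guidelines at comprehensive stroke centers, and the order sets and Manual of Procedures, which are not shown, may already require a scan first. Exclusion 26 removes many patients who would need an urgent start. In mice, a surrogate antibody did not raise surgical bleeding when combined with antithrombotics (Section 6.1.1), and Section 2.5.1 expects a low ICH risk. Waiting also delays antithrombotic treatment in every arm, placebo included.

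Most of this stands, and it limits the weight of the point. It does not remove it: the protocol states a specific safety rule, and that rule permits treatment before hemorrhage has been looked for.

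Several stronger readings are tempting but not supported:
- **No one at the site reads the CT.** Central reading is described as endpoint adjudication and does not exclude a local clinical read. The protocol simply does not require one before antithrombotics.
- **Section 8.5 forces a start before the CT.** That depends on how days are numbered, which is not defined, and the line may be only a data item. If the dosing day is day 0, the end of day 2 falls 48 to 72 h after dosing and there is no clash.
- **A count of participants at risk can be taken from the ICH rates in the protocol.** Those rates do not tell how many have an undetected hemorrhage and also start an antithrombotic in the gap. No figure in the protocol does.
- **The primary safety comparison is biased.** The rule is the same in all blinded arms. Any effect on the ICH rate or the utility cannot be quantified and may be nil.
- **The hold should outlast TS23 activity.** The activity data show why looking for hemorrhage first is sensible, but they do not establish a particular longer hold.

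**Conclusion.** The point holds as a modest patient-safety gap in the protocol text. Antithrombotics are permitted from 24 h, which is 2 to 10 h before an on-time CT at 26 to 34 h, and no section requires that CT to be obtained and read at the site first. The arithmetic is certain given the stated times. The practical consequence is not: it depends on how many participants start antithrombotics in that interval and on whether order sets, the Manual of Procedures or local guidelines are stricter, and the protocol settles neither. No number harmed and no between-arm bias is claimed. The change is worth making because it uses a scan that is already scheduled.

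**What to change.** In Sections 6.1.1 and 8.1, and in the order set, state that antithrombotics must not start until both conditions are met: at least 24 hours have passed since study drug, and the scheduled 30 (±4) h non-contrast CT has been obtained and read locally for intracranial hemorrhage. Allow an exception, at the investigator's judgement, for urgent need or a missed study CT.

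In Section 8.5, add to the antithrombotic line that the start comes after the 30 (±4) h CT has been read, and define day 2 relative to study drug administration. Central blinded reading remains the source of the endpoint. No additional mandatory scan and no new deadline are needed.

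The cost is a few sentences, an edited order set and a local read of an existing CT. The real downside is that the earliest routine start of antithrombotics moves 2 to 10 h later, plus reading time, in all arms. Doing the CT early in its window keeps this to about 2 h plus reading time.
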